A mechanism for increased AS in the uninjured population is over activation of the renin-angiotensin-aldosterone system (RAAS). Angiotensin II (ANG II), a hormone produced through RAAS, modulates vascular stiffness by reducing elastin, promotes collagen formation and increases oxidative stress. Due to decentralized cardiovascular autonomic control, individuals with SCI have a heightened reliance on RAAS to maintain and stabilize blood pressure (BP), especially during an orthostatic challenge. **Participants:** A total of 33 subjects, 22 individuals with SCI and 11 age-matched uninjured controls. **Objectives:** To study the hazardous effects of a highly activated RAAS on vasculature, the participant will be placed on a tilt table in the supine position and progressively tilted (30°, 45 ° and 60 ° for 10 minutes at each angle of tilt). PWV will be measured during supine and hormonal assessments (active plasma renin) will be assessed at supine and 60 degree tilt to determine if RAAS specific hormones contribute to increased AS in each cohort. The study aims are: 1) To investigate the influence of orthostatic change of BP and NE responses to orthostasis; and 2) To determine if increased reliance on the RAAS for orthostatic BP regulation contributes to differences in supine AS in individuals with SCI.

SPECIFIC AIMS:

Aim 1: *To investigate the influence of orthostatic change in BP on plasma renin responses to HUT.*

Hypothesis 1A: There will be an inverse relationship between the change in BP and change in plasma renin from supine rest to 60°HUT in individuals with high-level SCI.

Hypothesis 1B: There will be no relationship between the change in BP and change in plasma renin from supine rest to 60° HUT in persons with low-level SCI and uninjured controls.

Orthostatic Blood Pressure and Arterial Stiffness in Persons with Spinal Cord Injury: The Effect of the Renin-Angiotensin-Aldosterone System

Aim 2: To investigate the influence of orthostatic change in BP and NE on the RAAS responses to HUT.

Hypothesis 2A: There will be a linear relationship between the change in orthostatic BP and change in plasma NE concentration from supine rest to 60° HUT.

Hypothesis 2B: Plasma renin activity will be inversely related to plasma NE concentrations during HUT in persons with SCI.

Aim 3: To determine if increased reliance on the RAAS for orthostatic BP regulation contributes to differences in supine AS.

Hypothesis 3A: There will be significant group differences for change in plasma renin during HUT, in that plasma renin will be significantly increased during HUT in participants with high-level SCI, but will remain unchanged in individuals with low-level SCI and uninjured controls.

Hypothesis 3B: Change in plasma renin during the HUT maneuver will be directly associated with supine PWV in individuals with high-level SCI.

Hypothesis 3C: There will be no relationship between the change in plasma renin during the HUT maneuver and supine PWV in persons with low-level SCI and uninjured controls.

REVIEW OF LITERATURE:

After a SCI, descending sympathetic preganglionic neurons are disrupted causing loss of supraspinal regulation of cardiovascular function[1, 2],which results in numerous clinical issues. The level of the spinal lesion greatly influences the amount of cardiovascular regulation dysfunction after SCI. In individuals with injuries below T6, the sympathetic and parasympathetic control of the heart and splanchnic bed are intact, both of which are essential for short- and long- term BP regulation [2]. On the other hand, individuals with higher-level injuries, the parasympathetic control remains integral, while sympathetic autonomic control is lost (Krasnouk, 2009). This results in persistent hypotension and severe drops in BP when moving to the upright position (OH) [1, 3-7].

OH has a higher prevalence in individuals with cervical compared to individuals with thoracic lesions, irrespective of whether their lesion was complete or incomplete[8, 9]. According to a Consensus statement from the American Autonomic Society and American Academy of Neurology, OH is defined as a decrease in systolic BP (SBP) of 20+ mmHg and/or a fall in diastolic BP (DBP) of 10+ mmHg within 3-minutes of moving from supine to the upright position, with or without symptoms [10]. Interestingly, decreased plasma NE has been noted in individuals with cervical lesions when compared to individuals with thoracic injuries and controls [11-14]; and furthermore, there was no significant increase in NE level when individuals with tetraplegia underwent HUT [15, 16]. Additionally, lower levels of NE have been found to be associated with an increased incidence of OH in persons with SCI [17]. Individuals with

Orthostatic Blood Pressure and Arterial Stiffness in Persons with Spinal Cord Injury: The Effect of the Renin-Angiotensin-Aldosterone System

lesions below the cervical spine have normal to high levels of plasma NE concentrations [13, 14] and, as a result, are less prone to hypotension and OH [3, 18, 19].

Additionally, OH after SCI is thought to be largely related to inability to centrally regulate vascular tone [20]. The loss of the reflex vasoconstriction of the splanchnic bed and lower extremity vasculature results in venous blood pooling, which results in reduced blood volume in end-diastolic volume, leading to a decrease in cardiac output and left ventricular stroke volume [21]. In addition, due to paralysis of the lower extremities and physical inactivity, persons with SCI lose their ability to use skeletal muscle pump by activating muscle contraction. Individuals with paraplegia and uninjured controls demonstrated increased total peripheral resistance during a head-up tilt (HUT) compared to cervical injuries [22]. This suggests that the SNS was increased in controls and individuals with low-level injuries because they were able to increase venous return in order to maintain BP.

Although many individuals with SCI demonstrate OH, symptoms associated with OH decrease over time (light-headedness, blurred vision, fatigue, weakness, etc.) [19]. Evidence demonstrates that increased dependency on the RAAS is believed to play an integral part in reducing the severity of postural hypotension and the associated symptoms [12, 16, 19, 23, 24]. Renin was shown to increase in individuals with tetraplegia during HUT, an orthostatic challenge, at a much quicker and higher rise compared to individuals with thoracic injuries and uninjured controls [12, 23, 25].

The RAAS plays an essential role in maintaining long-term BP and is an enzymatic cascade in which renin is released into the blood and acts on angiotensinogen to form angiotensin I, which forms ANG II by the angiotensin converting enzyme (ACE) [26, 27]. Despite the important benefits of the RAAS in regulating BP homeostasis, recent evidence that chronic overproduction of this system may result in remodeling and restructuring of peripheral and coronary blood vessels by augmenting the generation of reactive oxygen species, [28, 29], accompanied by an increase in oxidative stress, and production of inflammation, thrombosis and fibrosis [28]. Recent evidence has demonstrated that the use of ACE inhibitors or ANG II receptor blockers (ARBs) reduce vascular remodeling [30-32], and diminish collagen production and increase the elastin to collagen ratio [31]. A meta-analysis demonstrated that the use of ARBs and ACE inhibitors decreased the risk of myocardial infarction, stroke, cardiovascular mortality and total mortality in uninjured subjects [33], suggesting that the excessive ANG II production may lead to an increased risk of CVD.

AS has been identified as an independent risk factor for CVD [31, 34, 35] and PWV is considered to be the gold standard measurement because of its high reliability and validity [36]. Increased AS has been documented in individuals with SCI compared to age-matched uninjured controls [2, 37-41], even after matching for age, body composition and activity level [20]. It is well appreciated that the increase in AS is due to the natural aging process [42], however, we recently reported that AS was not associated with age in the SCI population, suggesting premature cardiovascular dysfunction in persons with SCI [41].

Additionally, there is evidence supporting a direct linear association between AS and LOI, with AS increasing with ascending LOI [41]. In this same study, we reported that individuals with increased AS reported experiencing OH [41], because OH may cause structural vascular adaptations secondary to persistence and episodic hypotension [43]. Interestingly, our team recently demonstrated that there was significant inverse relationship between seated SBP and AS [41]; and furthermore, Wecht et al. (2005) demonstrated that anti-hypotensive agents (Midodrine and L-NAME) reduced orthostatic dependency on the RAAS because plasma renin

Orthostatic Blood Pressure and Arterial Stiffness in Persons with Spinal Cord Injury: The Effect of the Renin-Angiotensin-Aldosterone System

and serum aldosterone levels were comparable with baseline levels. We speculate that this may be related to a reliance on RAAS for orthostatic BP maintenance, which may have detrimental effects on AS[24]. Groothuis et al. (2010) demonstrated that ANG II contributed to increased supine leg vascular resistance in individuals with thoracic injuries (T4-T12), but did not contribute to AS in controls[44]. Although increased AS has been reported in individuals with SCI, controversy abounds and additional evidence is needed to gain a better understanding of impact of morphologic and physiologic vascular adaptations that occur following SCI on orthostatic BP regulation and AS.

SIGNIFICANCE OF RESEARCH:

Evidence has shown that PWV is increased 2-3 m/s in persons with SCI compared to able-bodied individuals [45, 46] which corresponds a staggering 40 year acceleration of age-related cardiovascular decline[47]. Evidence of causality suggests that decreases in AS, subsequent to administration of ARBs or ACE inhibitors, reduced vascular remodeling and decreased the risk of myocardial infarction, stroke and cardiovascular mortality in the uninjured population [33]. Additionally, the effects of OH on AS have not been studied in the SCI population, even though, persistent and episodic OH have been associated with elevated risk of stroke and cognitive deficits, including memory, processing speed and executive function in the uninjured population[48-51]. Documenting the impact of the RAAS on AS in the SCI population, will provide a necessary step in initiating a change in clinical treatment of hypotension and OH, which may lead to improved regulation and preservation of cardiovascular health and longevity.

RESEARCH DESIGN & METHODOLOGY:

Subjects– 22 individuals with SCI and 11 age-matched non-SCI controls will be recruited for eligibility to participate in the study. Individuals with SCI will be recruited from the Northern New Jersey SCI Model (NNJSCIS) System database, which contains over 1000 people with traumatic SCI. The control subjects will be recruited from prior study enrollment at Kessler Foundation and hospital personnel.

Inclusion Criteria:

- All subjects:
 - Between ages 21 and 70 years old.
- Additional Inclusion Criteria: SCI subjects:
 - Traumatic injury,
 - High-level injury: C1-T1 and Low-level injury: T6-T12,
 - Non-ambulatory,
 - American Spinal Injury Association Injury Scale (AIS) A, B or C,
 - 1+ year(s) post injury.

Exclusion Criteria:

Orthostatic Blood Pressure and Arterial Stiffness in Persons with Spinal Cord Injury: The Effect of the Renin-Angiotensin-Aldosterone System

- Acute illness or infection,
- Current smokers within 1 year,
- Documented history of controlled or uncontrolled hypertension or diabetes,
- Any other neurological condition other than a SCI (multiple sclerosis, Parkinson's disease),
- CVD (coronary heart disease, congestive heart failure, peripheral artery disease, stroke).

Procedure: All subjects will be asked to visit the Kessler Foundation (KF) laboratory for 1 day of testing. The study will take about 3 hours to complete per subject. Subjects will be asked to arrive between 8:00 am and noon at the KF testing facility after a normal breakfast and a good night sleep. Subjects will remain seated for 5-minute hemodynamic assessment. After, subjects will be transferred to the tilt table to lay supine for 10 minutes prior to another 5-minute hemodynamic assessment. Arterial stiffness, renin and NE will be collected in the supine position. Subjects will then be progressively tilted to 30°, 45° and 60° for 10 minutes at each angle and 5 minutes of hemodynamic assessments will be measured at each angle. At 60°, renin and NE will be collected.

- *Cardiovascular Assessments:* While the subject is seated 3 ECG electrodes will be affixed to the chest and abdomen for continuous monitoring of HR and respiration rate (RR). Brachial BP will be monitored at 1 minute intervals using a standard adult BP cuff placed at the right upper arm, and beat-to-beat finger arteriolar BP will be continuously monitored from the right middle finger throughout testing. MAP (mmHg) will be calculated from brachial BP using the formula: [systolic BP + (2 X diastolic BP)]/3. Beat-to-beat HR, RR and BP data will be viewed in real-time and stored for subsequent analysis using customized programs created with LabView graphical software.
- *Arterial Stiffness:* aPWV (aortic pulse wave velocity) will be measured using the SphygmoCor CPV system (AtCor Medical Pty Ltd., West Ryde, NSW., Australia) at the carotid and femoral sites measured from the participant's supra-sternal notch to each artery. The aPWV measurement will be taken in two steps: a tonometry reading of site A (carotid artery) with an ECG signal simultaneously recorded captured after 10 seconds of good data, followed by a 10 second reading of site B (femoral artery) with an ECG signal.
- *Tilt table:* will be used to perform an orthostatic provocation, which will be a progressive HUT from supine position to 30°, 45° and 60° for 10 minutes at each angle of tilt. Adjustment of the tilt table to each angle will be accomplished in less than 5 seconds, and subjects will be questioned at each angle of tilt regarding symptoms of syncope (i.e., blurry vision, dizziness, light-headedness, or nausea). The tilt table will be padded and motorized. Restraining straps will be used on the lower extremities and trunk to ensure subject safety during higher inclinations of HUT and to avoid lower-extremity muscle contractions in the control subjects. The straps will be wide and padded for subject comfort and to insure that stimulation of sympathetic spinal reflexes was not evoked.
- *Hormonal Assessment:* Blood will be drawn from a vein in the arm or hand twice each study visit to measure plasma renin level and NE. One sample of each will be taken in the supine position after baseline hemodynamic data collection and the other will be taken when tilted to 60°. Alcohol will be used to sterilize the area. A rubber band will be placed around the arm proximal to the vein. A small needle will be inserted into the vein to

Orthostatic Blood Pressure and Arterial Stiffness in Persons with Spinal Cord Injury: The Effect of the Renin-Angiotensin-Aldosterone System

collect blood. Once the blood has been collected, the needle will be removed and the puncture site will be covered. Samples will be immediately spun, down plasma separated and stored at -80 ° C for subsequent high performance liquid chromatography (HPLC) analysis of renin and NE concentrations which will be performed at the Bronx VA research lab.

Table 1. Protocol Timeline						
Time Point	Seated	Seated	Supine	30° Tilt	45° Tilt	60° Tilt
Time (min)	0-10	10-15	15-50	50-60	60-70	70-80
Heart Rate	Instrumentation	X	X	X	X	X
Breathing Rate		X	X	X	X	X
Blood Pressure		X	X	X	X	X
Blood Draw			X			X
Arterial Stiffness				X		

RISKS AND DISCOMFORTS:

1. Heart Rate, Arterial Stiffness and Blood Pressure: These are non-invasive procedures that involve minimal risk; however some subjects may experience discomfort when the ECG electrodes are removed from the skin and when the blood pressure cuffs are inflated.
2. Blood Draws: Subject may experience some discomfort when the needle is being place in the arm vein. Expected risks may include bruise or infection at the site of skin puncture, temporary faintness and rarely temporary loss of consciousness.
3. Tilt table: Subjects may feel dizzy, lightheaded or nauseous letting the staff passively reposition the subject from lying down to 30, 45 and 60-degree tilt. A staff member will be supporting the subject during this tilt, but if he or she feels uncomfortable, the staff will stop the test at any time.

DATA ANALYSIS:

Aim 1: To investigate the influence of orthostatic change in BP on plasma renin responses to HUT.

Hypothesis 1A: There will be an inverse relationship between the change in BP and change in plasma renin from supine rest to 60° HUT in individuals with high-level SCI.

Hypothesis 1B: There will be no relationship between the change in BP and change in plasma renin from supine rest to 60° HUT in persons with low-level SCI and uninjured controls.

Orthostatic Blood Pressure and Arterial Stiffness in Persons with Spinal Cord Injury: The Effect of the Renin-Angiotensin-Aldosterone System

Statistical Analysis: To determine the relationship between change in BP and change in plasma rennin, we will use Pearson's correlation coefficient or Spearman's correlation coefficient with alpha. The independent variable is change in SBP from supine rest to 60° HUT and the dependent variable is change in renin from supine rest to 60° HUT. The alpha level will be set at 0.05.

Aim 2: *To investigate the influence of orthostatic change in BP and NE on the RAAS responses to HUT.*

Hypothesis 2A: There will be a linear relationship between the change in orthostatic BP and change in plasma NE concentration from supine rest to 60° HUT.

Hypothesis 2B: Plasma renin activity will be inversely related to plasma NE concentrations during HUT in persons with SCI.

Statistical Analysis: To determine the relationship between change in BP and NE, we will use Pearson's correlation coefficient or Spearman's correlation coefficient with alpha. The independent variable is change in SBP from supine rest to 60° HUT and the dependent variable is change in NE from supine rest to 60° HUT. The alpha level will be set at 0.05.

Aim 3: *To determine if increased reliance on the RAAS for orthostatic BP regulation contributes to differences in supine AS.*

Hypothesis 3A: There will be significant group differences for change in plasma renin during HUT, in that plasma renin will be significantly increased during HUT in participants with high-level SCI, but will remain unchanged in individuals with low-level SCI and uninjured controls.

Statistical Analysis: Differences in change in plasma renin during HUT between groups will be analyzed using univariate group by ANOVA, with the interaction effect being the statistical effect of interest. The alpha level will be set at 0.05. The G*Power calculations indicate that with a total sample size of 33, there will be a power = 0.8.13 to detect the effect size.

Hypothesis 3B: Change in plasma renin during the HUT maneuver will be directly associated with supine PWV in individuals with high-level SCI.

Hypothesis 3C: There will be no relationship between the change in plasma renin during the HUT maneuver and supine PWV in persons with low-level SCI and uninjured controls.

Statistical Analysis: To determine the relationship between change in plasma renin and supine PWV, we will use Pearson's correlation coefficient or Spearman's correlation coefficient with alpha. The independent variable is change in renin from supine rest to 60° HUT and the dependent variable is PWV during supine rest. The alpha level will be set at 0.05.

Orthostatic Blood Pressure and Arterial Stiffness in Persons with Spinal Cord Injury: The Effect of the Renin-Angiotensin-Aldosterone System

STUDY COMPENSATION:

Subjects will receive \$100 for their participation.

PUBLICATION OF RESEARCH:

It is anticipated that the observations made in this study will be presented at National meetings and will be submitted for publication in peer-reviewed journals, including those in the fields of Spinal Cord Medicine.

COST ANALYSIS:

Kessler Foundation will be not responsible for any costs associated with this project. This protocol will be funded by the NJ Commission on Spinal Cord Research (CSCR18FEL010).

REFERENCES:

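### Controls are matched on age only and come from a different source than the SCI participants, so a sex imbalance could bias the control-versus-SCI contrast in Hypothesis 3A

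*Combined protocol and SAP*

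**What the plan says.** The summary describes the sample as "A total of 33 subjects, 22 individuals with SCI and 11 age-matched uninjured controls", and the Subjects paragraph repeats age as the only matching factor: "22 individuals with SCI and 11 age-matched non-SCI controls will be recruited for eligibility to participate in the study".

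The two samples have different sources. SCI participants come from a Model System database, "which contains over 1000 people with traumatic SCI". For the others, "The control subjects will be recruited from prior study enrollment at Kessler Foundation and hospital personnel".

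The one inclusion criterion common to everyone is "Between ages 21 and 70 years old". No inclusion or exclusion criterion, quota or analysis mentions sex.

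Hypothesis 3A states: "There will be significant group differences for change in plasma renin during HUT". It predicts a rise in the high-level SCI group and no change in the low-level group or the controls. The Data Analysis section says that this will be "analyzed using univariate group by ANOVA, with the interaction effect being the statistical effect of interest". It names no covariate.

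**The concern.** The plan already restricts several sources of vascular variation: age by matching, and smoking, hypertension, diabetes and cardiovascular disease by exclusion. Sex is left free. Nothing in the documents indicates that staff and earlier volunteers have the same sex mix as a traumatic-injury database, and nothing requires the 11 selected controls to reflect the mix of the 22 SCI participants.

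If men and women differ in renin change on tilt, an unadjusted comparison of group means would count part of that difference as an effect of injury. What is at stake is the control-versus-SCI part of 3A: its estimate could be shifted, and the overall F test could reject somewhat more often than 5% when no group effect exists.

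**Working it through.** **The plan's own figure.** Power for 3A with 33 subjects is printed as 0.8.13, read here as 0.813. No effect size is given, so it cannot be reproduced. Solving a one-way ANOVA on renin change (3 groups, df 2 and 30, alpha 0.05) for power 0.813 gives f = 0.577. If only the high-level group differs, this is a difference of f × 3/√2 = 0.577 × 2.121 = about 1.22 SD. That is the yardstick below. With only two blood draws, a group-by-time interaction is the same F test as a one-way ANOVA on the change, so either reading of the 3A sentence leads to this calculation.

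**Inputs.** From the documents: 22 SCI, 11 controls, alpha 0.05, no covariate. Assumed: 11 high-level and 11 low-level participants, 80-90% men in SCI, 30-80% men in controls, and a sex effect on renin change of 0-0.8 SD that is the same in every group.

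**Bias.** Bias in SD units = (share of men in SCI − share of men in controls) × sex effect. The rejection rates are from simulated studies with 11 per group and no true group effect.

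| Men in SCI | Men in controls | Sex effect (SD) | Bias (SD) | F test rejects |
|---|---|---|---|---|
| 80% | 80% | any | 0 | 5% |
| 80% | 50% | 0.5 | 0.30 × 0.5 = 0.15 | about 6% |
| 80% | 50% | 0.8 | 0.30 × 0.8 = 0.24 | about 8% |
| 80% | 30% | 0.5 | 0.50 × 0.5 = 0.25 | about 8% |
| 90% | 30% | 0.5 | 0.60 × 0.5 = 0.30 | about 10% |
| 90% | 30% | 0.8 | 0.60 × 0.8 = 0.48 | about 17% |

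The largest bias is 0.48/1.22 = 39% of the effect implied by the stated power.

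**How easily an imbalance arises.** The chance of 6 or fewer men among 11 controls is 5% if the control pool is 80% male, 33% if it is 65% male and 73% if it is 50% male.

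**Does it mimic 3A?** Both SCI groups come from one database, so a control imbalance leaves the difference between them alone. In the simulations, a significant F test with the high-level group differing from both others in the same direction occurred in 1.0% to 1.5% of studies, against 1.0% with no sex effect.

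**Adjusting afterwards.** With sex as a covariate and an additive sex effect, rejection returned to 4.8%-5.3%, including in the worst cell. At a 1.22 SD high-level effect, adjusted power was 0.76-0.78 with imbalance, against 0.785 with an equal mix.

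The cost falls on the precision of the control contrast. Its variance is multiplied by 1 + [D²/W]/(1/11 + 1/22). D is the difference in the share of men, and W is the within-group sum of squares for sex, about 10 × the sum of p(1−p) over the three groups. The term 1/11 + 1/22 is 0.136.

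- 80% vs 50%: W = 10 × (0.16 + 0.16 + 0.25) = 5.7; 1 + (0.09/5.7)/0.136 = 1.12 (simulated median about 1.11).
- 80% vs 30%: W = 10 × (0.16 + 0.16 + 0.21) = 5.3; 1 + (0.25/5.3)/0.136 = 1.35 (simulated median about 1.33).
- 90% vs 30%: W = 10 × (0.09 + 0.09 + 0.21) = 3.9; 1 + (0.36/3.9)/0.136 = 1.68 (simulated median about 1.73).

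In the worst tenth of samples the factor reached 1.9 (80% vs 30%) or 2.8 (90% vs 30%).

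**The case against.** The strongest reply is that every input to the size is assumed. The documents give no sex mix for the database, the staff or the earlier volunteers, and say nothing about sex and renin. The investigators choose only 11 controls and could balance them informally. Age-matched controls are ordinary in a small single-visit study, and the literature review also mentions matching on body composition and activity, so singling out sex is partly a matter of preference. That stands as a limit on how confidently any size can be stated, and it is why the range starts at no bias. It does not remove the gap, because the plan does not require such balancing.

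A reader might infer three stronger things that the documents do not support.

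- *That the groups will differ in sex mix.* Different sources make this possible; no figure shows it.
- *That 3A as a whole, or the other hypotheses, are undermined.* The high- versus low-level contrast does not depend on control recruitment. The remaining hypotheses concern relationships, most of them stated by group, rather than differences in group means.
- *That 11 controls make later adjustment useless.* Adjustment restores the error rate under an additive sex effect. What it loses is precision, and under strong imbalance it rests on few women: if the SCI sample is 90% male, the chance of two or fewer women among the 22 is 62%.

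**Conclusion.** The point holds as a modest design weakness. The matching rule and the unadjusted ANOVA leave the control-versus-SCI contrast in renin change open to confounding by sex. Under the stated assumptions the bias lies between 0 and about 0.48 SD, and the chance of a false overall rejection between about 5% and 17%; the upper ends need both a strong imbalance and a large sex effect. The direction cannot be set from the documents.

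A chance sex imbalance between the two SCI groups remains possible, but it is not caused by the control source. This is a worthwhile improvement rather than a flaw that threatens the study, and confidence in its size is low.

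**What to change.** In the summary and in the Subjects paragraph, change *age-matched* to *age- and sex-matched*, and frequency-match the 11 controls to the sex mix of the 22 SCI participants. For example, 18 men among 22 would mean 9 men among 11.

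In the Data Analysis section, report sex by group and prespecify a sensitivity analysis of 3A with sex as a covariate. With balanced groups the covariate costs almost nothing: power 0.812 against 0.813 at f = 0.577, with df 29 instead of 30. Matching at recruitment is preferable to adjustment alone because it avoids the variance inflation of about 1.1 to 1.7 on the control contrast.

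The cost is a few lines of text and slightly slower control recruitment. The sample size stays at 33 and no procedure changes.

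### A four-hour arrival window after an unstandardised breakfast adds avoidable noise, mainly to the single supine PWV value, and is cheap to tighten

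*Combined protocol and SAP*

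**What the plan says.** Research Design & Methodology, Procedure, gives the only pre-test condition in the available text: "Subjects will be asked to arrive between 8:00 am and noon at the KF testing facility after a normal breakfast and a good night sleep". There is a single visit: "All subjects will be asked to visit the Kessler Foundation (KF) laboratory for 1 day of testing". For sampling it says "Arterial stiffness, renin and NE will be collected in the supine position" and then "At 60°, renin and NE will be collected". Table 1 places the supine stage at minutes 15-50 and the 60° stage at minutes 70-80.

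Two related controls exist. Participants lie supine for 10 minutes before the supine haemodynamic assessment, and the exclusion criteria list "Current smokers within 1 year". Nothing is said about the content or timing of breakfast, caffeine, or recording of start time or last meal.

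On recruitment, the SCI participants come from a model-system database. For the others, "The control subjects will be recruited from prior study enrollment at Kessler Foundation and hospital personnel". No rule links appointment times to group.

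In Data Analysis, Aims 1 and 2 and Hypotheses 3B/3C use Pearson or Spearman correlations without adjustment, and Hypothesis 3A uses an ANOVA with no covariate. For 3B/3C: "The independent variable is change in renin from supine rest to 60° HUT and the dependent variable is PWV during supine rest".

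**The concern.** Every endpoint is measured on one morning per person, in groups of about 11, under conditions left to the participant's habits and the appointment diary. Variation in time since eating, caffeine and clock time goes into the measurements with nothing in the design to limit it and nothing in the analysis to account for it.

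The protocol's own physiology makes the meal relevant. Its Review of Literature says that splanchnic control is intact in injuries below T6 and that sympathetic control is lost in higher injuries. It attributes part of the orthostatic fall to pooling in the splanchnic and leg vessels. A recent meal loads the splanchnic bed, so it could plausibly change the response to tilt.

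At stake is the precision of small-sample correlations. Noise pulls correlations towards zero. That weakens 1A and 3B, which predict an association, and makes the predictions of no association in 1B and 3C easier to appear to confirm.

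**Working it through.** **Inputs.** Arrival 08:00-12:00 and a visit of about 3 hours (Procedure). Supine at minutes 15-50 and 60° at minutes 70-80 (Table 1). N = 33, with 22 SCI and 11 controls (Subjects). Alpha 0.05 (Data Analysis). An 11/11/11 split is assumed, because the division of the 22 SCI participants by level is not stated.

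**1. Clock time.** Taking minute 0 as arrival:
- Supine stage: 08:00 + 15 min = 08:15 to 12:00 + 50 min = 12:50.
- 60° stage: 08:00 + 70 min = 09:10 to 12:00 + 80 min = 13:20.
- Difference between two participants at the same protocol minute: up to 12:00 − 08:00 = 4 h.

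Table 1 does not say that minute 0 is arrival. It covers 80 of about 180 minutes, so about 100 minutes are unplaced. If all 100 came first, the supine stage would run from 09:55 to 14:30. The clock times move, but the 4-hour spread stays as long as the delay is the same for everyone.

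**2. Time since eating.** The documents give no breakfast time, so only a range can be shown. If everyone ate between 07:00 and 08:00 whatever their slot, and minute 0 is arrival, the supine stage falls between 08:15 − 08:00 = 0.25 h and 12:50 − 07:00 = 5.8 h after the meal. If everyone ate at the same interval before arriving, the arrival window adds no spread at all. The truth may lie anywhere between.

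**3. Which endpoints are exposed.** Within one person the supine and 60° samples are 70 − 50 = 20 to 80 − 15 = 65 minutes apart. A constant time-of-day offset therefore largely cancels in the changes in systolic BP, renin and NE. An effect of a recent meal on the response to tilt does not cancel. Supine PWV is not a change score and has no such protection.

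**4. Illustration for 3B (assumed sizes).** With n = 11 and two-sided 0.05, the critical correlation is t/√(9 + t²) with t = 2.262, which gives 0.602. Extra independent variance v in PWV alone reduces a true correlation r to r/√(1 + v). With r = 0.70 and v = 0.20, this is 0.70/√1.20 = 0.639. Simulated power (bivariate normal, 400,000 samples) is 73% at 0.70 and 61% at 0.639. The Fisher approximation Φ(atanh(r)·√8 − 1.96) gives 69% and 57%, a fall of the same size.

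**5. Illustration for 3A (assumed sizes).** The printed power, 0.8.13, is read as 0.813. It cannot be reproduced because no effect size is given. Solved backwards with the noncentral F distribution, 0.813 for a one-way comparison of change scores in three groups of 11 needs Cohen's f = 0.577. Extra variance v gives f/√(1 + v):

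| Extra variance | f | Power |
|---|---|---|
| 0 | 0.577 | 0.813 |
| 10% | 0.551 | 0.773 |
| 20% | 0.527 | 0.734 |
| 30% | 0.506 | 0.697 |
| 50% | 0.472 | 0.630 |

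The documents do not show which row applies.

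**The case against.** The strongest reply is that the plan already asks for arrival by noon, breakfast, a good night's sleep and supine rest, and excludes recent smokers, while the harm alleged is unmeasured. Much of this stands. No passage says that meals, caffeine or clock time alter renin, NE or PWV; that is general physiology taken as an assumption, and the splanchnic argument is an inference from what the protocol says about posture. Caffeine is not mentioned at all, and an instruction could appear in the consent material, which is outside the text considered here. Most endpoints are change scores, and no between-group test of PWV is planned.

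A reader might go further and infer a biased group comparison in 3A: on-site controls tested early, high-level SCI participants tested late after longer morning care and transport. The documents do not support this. They hold no arrival data, and controls also come from earlier studies. Even the direction is unclear: with a fixed breakfast time, late arrivals would be tested longer after eating, which would reduce a meal effect in the group thought most sensitive to it. A 0.5 SD shift in one group would raise false rejection in 3A from 5% to 19.3%, but nothing in the documents points to 0.5 rather than 0. Nor would a group difference in start time by itself bias the correlations within groups in 3B/3C.

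The objection does not remove the basic gap. The stated rule allows the variation, and the available text neither limits nor records it.

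**Conclusion.** The concern holds as a point about avoidable noise. The rule permits up to 4 hours of clock-time difference at the same step (a common delay between arrival and minute 0 is assumed) and an unknown spread in time since eating. Supine PWV in 3B/3C is most exposed. The tilt responses are exposed only so far as a recent meal changes them. The power losses above are scenarios, not estimates. A group difference in start or meal time remains possible because nothing balances it, but its existence, direction and size cannot be derived from the documents. This is a cheap improvement, not a flaw that invalidates the design.

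**What to change.** Replace the arrival sentence with one pre-test condition common to all three groups: a standard light breakfast finished at least a fixed interval before the supine measurements, and no caffeine on the test morning. The investigators should choose the interval and state it.

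Keep the morning window, but spread arrival slots evenly across the three groups, or give age-matched participants the same slot. One narrow slot for everyone is not needed and could be hard on participants with long morning care.

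Record time of last meal and start time on the case report form. In Data Analysis, prespecify a sensitivity analysis, for example partial correlations for 3B/3C adjusted for one of these times at a time. With about 11 per group, adjustment for several covariates would be weak, so control should come mainly from the design.

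The cost is one added participant instruction, two recorded times and slightly less scheduling flexibility. No procedure, staff or participants are added.
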